#### 6.1.1 ADMINISTRATION AND/OR DOSING

N/A

#### 6.2 FIDELITY

##### 6.2.1 INTERVENTIONIST TRAINING AND TRACKING

Ensuring fidelity to the ADRD-PC will be the responsibility of all site-based investigators. Our approach is based on NIH Behavior Change Consortium standards, with elements relevant to study design, interventionist training and standard operating procedures, and tools to support delivery of the ADRD-PC intervention.

| Types of Fidelity                  | Procedures to Ensure Fidelity   | Fidelity Monitoring  |
|------------------------------------|---|--|
| Study Design                       | 
 
Intervention based on a well-defined protocol
 
Standardized tools and templates
 
   | 
 
Protocol review and version control supported by Palliative Care Research Cooperative group
 
  |
| Standardized Training and Delivery | 
 
Training of Site-PIs on study protocol and SOPs
 
Training of Site-CRCs on study protocol and SOPs
 
Training of PC clinicians to deliver ADRD-PC
 
Audio-recorded training modules for consistent re-training or for new personnel
 
ADRD-tools and templates
 
          | 
 
Training material review by Palliative Care Research Cooperative group
 
Completed training
 
Post-training evaluation for PC clinicians (threshold score 80%)
 
Delivery of tools and templates to all study sites
 
   |
| ADRD-PC Intervention Enactment     | 
 
Monthly conference calls (led by [name]) with site PC clinicians
 
Monthly conference calls (led by UNC Project Manager) with site CRCs and site PIs=Utilization of ADRD-PC Program with standardized content areas
 
Documentation of clinical encounters in site medical record
 
 | 
 
Site-CRC tracking of completion of 4 ADRD-PC components: a) PC encounter, b) caregiver education, c) delivery of PC Plan to caregiver and primary or post-acute care provider (PACP) , and d) completion of 2 transitional care calls.
 
Threshold score 80% of dyads with completion of 4 ADRD-PC components.
 
Site specific feedback when fidelity drops below threshold.
 
Review 10% random of deidentified ADRD-PC encounter notes to ensure adherence,
 
 |

|  |  |   |
|--|--|---|
|  |  | scored for quality of content across 4 clinical domains |
|--|--|---|

### 6.3 MEASURES TO MINIMIZE BIAS: RANDOMIZATION AND MASKING

Randomization will occur following the enrollment interview, with the dyad as the unit of randomization and analysis. Allocation will be concealed prior to randomization. Randomization will be generated within REDCap software, and transmitted by the Site-CRC to the PC team to initiate ADRD-PC (intervention) or to deliver dementia caregiver educational material (control).

CRCs who collect outcome data will be masked to study arm in family caregiver interviews. Since the EHR will have ADRD-PC palliative care encounters, Site-CRCs will complete follow-up EHR reviews only after 60-day follow-up interviews. [name] (PI) will remain masked to study arm assignments to minimize bias in study procedures and analysis.

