| Description of Sites/Facilities    | 5 medical centers with interdisciplinary specialty palliative care teams - University of North Carolina (UNC), University of Indiana (IU), University of Colorado (UC), Massachusetts General Hospital (MGH), Emory University (EU) |
| Description of Study Intervention: | The ADRD-PC program includes 3 main components: dementia-specific palliative care consultation, standardized caregiver education, elements of evidence-based transitional care.   |
| Study Duration:                    | 60 months   |
| Participant Duration:              | 60 days post hospitalization  |

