## 5.2 EXCLUSION CRITERIA

Dyads will be excluded if (1) the LAR is not a family caregiver, (2) the patient currently receives palliative care or hospice, (3) patient or caregiver would be unduly stressed, or (4) dyad is not successfully randomized.

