- 3) **Transitional care** will be provided by the palliative care team. Pre-discharge, the palliative care team will explore **adequacy of patient and caregiver support for practical, emotional and spiritual needs**. Based on needs, they will recommend **community-based support services**. Examples could include community palliative care, hospice, home health, specialty geriatric or dementia clinics, adult day care or Alzheimer caregiver support groups. Near discharge, a member of the palliative care team will create a templated Palliative Care Plan and provide copies to the primary or post-acute care provider (PACP) AND the family caregiver. This document will summarize recommendations in the four domains and provide contact information for the palliative care team for follow-up questions. Post-discharge, a designated palliative care team member – usually a social worker or nurse coordinator – will call the family caregiver within 72 hours and again within 2 weeks after discharge. These calls may also be facilitated by a site CRC. The purpose of these calls will be to support implementation of the Palliative Care Plan and access to post-acute

supportive services. Calls will also be used to solicit concerns, offer emotional support, and make recommendations to help the caregiver overcome barriers to services.

**Control condition:** Patient-family caregiver dyads randomized to the control arm will receive educational materials from the Alzheimer's Association, specifically designed for late-stage ADRD caregivers. The patient will receive usual hospital and post-acute care.

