Analysis to Meet Aim 1: We will compare control and intervention arms on hospital transfers (primary outcome) during 60 days post-discharge. This count outcome is defined as the total number of emergency room visits plus hospital admissions per at-risk patient-days. We will use Poisson regression with empirical 'robust' standard errors allowing for overdispersion to compare the transfer rates between groups. We will use the length of follow-up as the offset variable, which means that patients who have data only from the 30-day interview will be included. The primary analysis will be based on the model with main effects for treatment group, study site, GDS Stage and patient and caregiver sex as biological variables. Evaluation of the treatment effect will be based on a Wald test. The covariate-adjusted treatment effect will be quantified as an incidence rate ratio (IRR) with a 95% confidence interval. Considering that over 60% of patients in the pilot study did not have any hospital transfers, we will conduct a sensitivity analysis for the treatment effect on 60-day hospital transfers with a marginalized zero-inflated Poisson (MZIP) model, which may modestly increase power. Secondary Poisson and MZIP analyses will compare study arms for 30-day hospital transfer rates. An exploratory analysis will be conducted to examine interactions of treatment group with study site, sex, race / ethnicity and GDS Stage, respectively, on 60-day hospital transfers. While the proposed study is powered to detect whether or not ADRD-PC is effective, a much larger study would be needed to have adequate power to detect differences by sex or GDS Stage and would be justifiable only after the completion of this initial trial. An interaction model will be used if an omnibus test for interactions is statistically significant at the 0.05 level. A second exploratory analysis will evaluate a dose-response effect of the intervention on the hospital transfer rate. A dose for patients receiving the intervention is defined as the number of key intervention components used in fidelity monitoring (range 0 to 4 with 0 for controls). The dose effect is the incremental benefit of adding a single component; its rescaling gives the per-protocol effect of the full intervention.

---

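### Section 6.3, read literally, routes control dyads through the trained palliative care team, and controls' inpatient palliative care exposure is not recorded, so contamination can be judged only indirectly

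*Combined protocol and SAP*

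**What the plan says.** **Allocation and delivery.** Section 6.3 randomizes "with the dyad as the unit of randomization and analysis" and says that the result is "transmitted by the Site-CRC to the PC team to initiate ADRD-PC (intervention) or to deliver dementia caregiver educational material (control"). Section 6.2.1 lists "Training of PC clinicians to deliver ADRD-PC" among the fidelity procedures.

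**Control condition.** Section 6.1 gives controls Alzheimer's Association material and adds: "The patient will receive usual hospital and post-acute care". The synopsis describes the sites as "5 medical centers with interdisciplinary specialty palliative care teams". The only exclusion that bears on this (section 5.2) applies when "the patient currently receives palliative care or hospice". It does not reach a consult ordered after randomization.

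**What is recorded.** The section 6.2.1 fidelity table provides for "Site-CRC tracking of completion of 4 ADRD-PC components", under enactment of the intervention. Section 8.1 says that data collection is the same in both arms. Its interview list includes hospice and community palliative care use. Its EHR list includes the Palliative Care Domain Index items, documented prognosis discussion, and documented goals-of-care decision-making. An inpatient palliative care consult is in neither list, nor in the Schedule of Activities (section 1.2).

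**What is analyzed.** The second exploratory analysis in section 9.4.2 uses a dose with "range 0 to 4 with 0 for controls" and rescales its slope to a per-protocol effect of the full intervention.

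**The concern.** One palliative care team per site serves both arms, has been trained in the intervention, and on a literal reading meets control caregivers to hand over their material. Usual care at these hospitals can also bring a consult from that team, and the plan does not address it. If some controls receive part of what ADRD-PC offers, the primary contrast shrinks.

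The difficulty is mainly one of interpretation. Without a direct record of inpatient palliative care encounters by arm, a null or weak result leaves open how far the arms actually differed in exposure. The items that would move with contamination are themselves trial outcomes. They cannot separate a consult by the trained team from good care by the attending physician. In the exploratory dose analysis, an exposed control coded 0 is misclassified.

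**Working it through.** **Inputs.** Table 3 (section 9.2): control rate 0.53; differences 0.25 and 0.20; overdispersed power 0.81 and 0.60 at 15% dropout, 0.76 and 0.55 at 25%. Per-arm n is 180 and 159: 424 × 0.85 / 2 = 180.2 and 424 × 0.75 / 2 = 159.0. Two-sided alpha is 0.05. The overdispersion factor φ and the contamination fraction c are not given.

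**Step 1: reproduce Table 3.** Power = Φ( (λ0 − λ1) / √(φ(λ0 + λ1)/n) − 1.96 ).

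| n per arm | Difference | Poisson, φ = 1 (stated) | φ = 1.70 (stated, overdispersed) |
|---|---|---|---|
| 180 | 0.25 | 0.961 (0.96) | 0.815 (0.81) |
| 180 | 0.20 | 0.825 (0.82) | 0.602 (0.60) |
| 159 | 0.25 | 0.939 (0.95) | 0.766 (0.76) |
| 159 | 0.20 | 0.776 (0.79) | 0.550 (0.55) |

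The Poisson rows agree within 2 points. One back-solved φ of about 1.70 reproduces all four overdispersed values. The reproduction needs no allowance for contamination.

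**Step 2: add contamination.** Suppose a fraction c of controls gets the full effect, beyond any exposure already contained in 0.53. The control rate becomes 0.53 − 0.25c and the intervention rate stays at 0.28. With n = 180 and φ = 1.70:

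| c | Control rate | Difference | SE | Power | IRR |
|---|---|---|---|---|---|
| 0 | 0.530 | 0.250 | 0.0875 | 0.815 | 0.528 |
| 10% | 0.505 | 0.225 | 0.0861 | 0.743 | 0.554 |
| 20% | 0.480 | 0.200 | 0.0847 | 0.656 | 0.583 |
| 30% | 0.455 | 0.175 | 0.0833 | 0.556 | 0.615 |

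Worked line for 20%: 0.200 / √(1.70 × 0.76 / 180) = 2.361; 2.361 − 1.960 = 0.401; Φ(0.401) = 0.656. In this linear model a half effect in 20% of controls equals a full effect in 10%, so power would be 0.743.

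**Step 3: dose analysis, illustration.** Assume a linear effect of 0.25/4 = 0.0625 per component. Assume also that 77% of intervention dyads receive 4 components and the rest 3 (77% is the pilot fidelity for the two calls, section 4.3), and that 20% of controls receive 2 components but are coded 0. With equal arms:
- mean coded dose = 0.5 × 3.77 = 1.885
- variance of coded dose = 0.385 × 16 + 0.115 × 9 − 1.885² = 3.642
- covariance with the true effect = 0.2040
- slope = 0.2040 / 3.642 = 0.0560, rescaled × 4 = 0.224 instead of 0.25

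With 30% of controls exposed, the rescaled effect is 0.211.

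**The case against.** **The sentence in 6.3 can be read otherwise.** Delivery of the control material may attach to the Site-CRC. Section 6.1 names the palliative care team for each intervention element but names nobody for the control material, and the Schedule of Activities marks the palliative care visits as intervention only. This stands: the point rests on the literal reading, and the text needs clarifying in either case.

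**Contamination may be small.** Section 2.2 says that palliative care is rare in ADRD. In the pilot (section 4.2) the arms separated widely: domain index 7.6 vs 2.7, prognosis discussion 90% vs 3%. Pilot controls also had usual care, and 0.53 appears to be the pilot control rate, so only exposure beyond pilot levels would dilute the planned difference. This stands. That controls may be consulted is an inference from the plan's silence.

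**A full effect is an extreme assumption.** ADRD-PC also includes the booklet, the written care plan and two calls, and an ordinary consult is not shown to supply them. This stands too; Step 2 gives the upper end for each c.

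**Stronger readings that the documents do not support.** A reader might infer that contamination would be invisible. It would not be: the domain index, the prognosis and goals-of-care items, and post-discharge palliative care or hospice use are collected in both arms. If the first three separate as in the pilot, contamination is a poor explanation of a null. A reader might also take Table 3's 0.20 row and conclude that 20% contamination cuts power to 0.60. That row compares 0.53 with 0.33. Contamination lowers the control rate, giving 0.48 vs 0.28 with a smaller variance, and power is about 0.66. Nor does the fixed dose of 0 touch the primary analysis, which does not use dose.

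**Conclusion.** The point holds in a limited form. On its literal wording, section 6.3 brings the trained team into contact with control dyads. No rule covers inpatient palliative care for controls after randomization. Neither a consult nor component receipt in controls is listed for collection, so contamination can be assessed only through outcomes that have other causes.

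The size is unknown because the documents give no rate. Under the assumptions shown (full effect, exposure beyond the pilot level, φ about 1.70, 180 per arm, planned difference 0.25), overdispersed power falls from about 0.81 to 0.74, 0.66 and 0.56 at 10%, 20% and 30%. Contamination biases toward no difference and would not create a false benefit. The intention-to-treat comparison remains valid. The dose misclassification is confined to an exploratory analysis. The change is worth making because it is cheap and makes a null result easier to interpret.

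**What to change.** 1. **Section 6.3.** Send the palliative care team intervention allocations only. Have the control material delivered by the Site-CRC who already handles the allocation, and state that this person does not conduct the masked outcome interviews. Site delivery is preferable to mailing from the coordinating center: caregiver contact details are held at the sites (section 10.1.3), and the PI, who must stay masked, leads the study from the same institution as the coordinating center.
2. **Section 8.1, EHR review, both arms.** Add any inpatient specialty palliative care encounter in the index stay or a readmission, its date, and whether the ADRD-PC Note Template was used. Report it by arm. Section 6.3 already places this review after the 60-day interview, so interview masking is unaffected.
3. **Section 9.4.2.** Keep the dose analysis as planned and add a sensitivity version that uses documented components in both arms. This requires the four components to be abstracted for controls as well. State that consulted controls may be sicker, so this version is open to confounding by indication and does not replace the planned one.

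Usual care is not restricted, and intention-to-treat stays primary. The cost is a short addition to an abstraction already done for every dyad, a small delivery task for site research staff, and one more exploratory analysis.

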## 7 STUDY INTERVENTION/EXPERIMENTAL MANIPULATION DISCONTINUATION AND PARTICIPANT DISCONTINUATION/WITHDRAWAL

### 7.1 DISCONTINUATION OF STUDY INTERVENTION/EXPERIMENTAL MANIPULATION

Due to the low risk of harm to study participants anticipated for this intervention, no interim analyses for efficacy or a priori stopping rules are planned. During the first DSMB meeting, in coordination with the NIA Program Official, the DSMB members will be asked to consider and recommend possible a priori stopping rules, if any, based on adverse event reporting.

### 7.2 PARTICIPANT DISCONTINUATION/WITHDRAWAL FROM THE STUDY

Participants are free to withdraw from participation in the study at any time upon request. An investigator may discontinue a participant from the study for the following reasons:

- Significant study intervention non-adherence
- Lost-to-follow up; unable to contact subject (see **Section 7.3, Lost to Follow-Up**)
- Any event or medical condition or situation occurs such that continued collection of follow-up study data would not be in the best interest of the participant

The reason for participant discontinuation or withdrawal from the study will be recorded on the Case Report Form (CRF). Subjects who sign the informed consent form and are randomized but do not initiate either the intervention or control procedures may be replaced.

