## 4 STUDY DESIGN

### 4.1 OVERALL DESIGN

Study design is an RCT conforming to SPIRIT and CONSORT statements for trial methods and protocol. Our approach uses NIA standards for a multi-site efficacy trial (Stage II) of a protocolized behavioral intervention, while incorporating pragmatic features to support sustainability and future dissemination. We will use 1:1 randomization of patient-caregiver dyads with concealed allocation until study assignment. Research will occur at 5 geographically diverse sites of the Palliative Care Research Cooperative (PCRC) network, with study leadership and centralized IRB at UNC. Sites will enroll N=424 dyads of hospitalized patients with late-stage ADRD (GDS 6-7 or GDS 5 with significant co-morbidity) with their family caregivers. Sites will additionally enroll N=50 dyads that identify as Hispanic/Latino. Intervention dyads will receive the ADRD-PC program of i) dementia-specific palliative care, ii) standardized caregiver education, and iii) transitional care. Control dyads will receive publicly available educational material on dementia caregiving. Outcomes will be measured at 30 days (interim) and 60 days post-discharge. The primary outcome will be 60-day hospital transfers, defined as visits to an emergency department or hospitalization (**Aim 1**). Secondary patient-centered outcomes will be symptom treatment, symptom control, use of community palliative care or hospice, and new nursing home transitions (**Aim 2**). Secondary caregiver-centered outcomes will be communication about prognosis and goals of care, shared decision-making about hospitalization and other treatments, and caregiver distress (**Aim 3**). The Principal Investigator

and outcome assessors will be masked; as in most behavioral interventions clinicians and participants cannot be masked to study arm. Analyses will use intention-to-treat, and pre-specified exploratory analyses will examine effects of sex as a biologic variable, race / ethnicity, and GDS stage.

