#### 9.3 POPULATIONS FOR ANALYSES

N/A

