#### 9.4 STATISTICAL ANALYSES

##### 9.4.1 GENERAL APPROACH

**Analysis:** Descriptive analyses of variables will examine distributions, influential data points, and missing data. Means (standard deviations) will be reported for continuous variables and frequencies (percentages) for categorical variables. Continuous variables (e.g., PC Domain Index, etc) that are poorly distributed may be transformed or analyzed using non-parametric

tests. We anticipate missing data on independent variables will be minimal. We will use simple mean and mode imputation for those variables included in regression models if less than 5% of patients have missing data; else, conditional (i.e., regression) imputation will be used. Available case analysis will be conducted for 30-day outcomes. Missing 60-day dichotomous outcomes will be multiply imputed if missingness exceeds 10%. Caregiver data collection is completed after deaths as in our prior ADRD research. Primary analysis will use intention-to-treat analysis. We will evaluate the effectiveness of randomization by comparing intervention and control participants on baseline measures. Variables that are not equally distributed between arms could potentially bias results. We will include these variables in each initial model and use a change-in-effect method for determining whether they are confounders. If removing any of these variables from the model does not appreciably change the regression coefficient estimate of the intervention group variable, we will not need to include them in the final model. Given our randomized design, we anticipate little confounding. A priori exploratory analyses will examine effects by sex as a biological variable, race / ethnicity, and GDS stage.

---

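### Section 7.2 lets a randomized dyad be discontinued from the study for undefined non-adherence and lets non-starters be replaced; intention-to-treat is promised, but nothing requires outcome collection to continue

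*Combined protocol and SAP*

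**What the plan says.** Section 7.2 contains two permissions that act after randomization.

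- **Discontinuation.** "An investigator may discontinue a participant from the study for the following reasons", and the first reason listed is "Significant study intervention non-adherence". No threshold is given, and the action is discontinuation from the study rather than from the intervention.
- **Replacement.** "Subjects who sign the informed consent form and are randomized but do not initiate either the intervention or control procedures may be replaced". Nothing is said about whether the original dyad keeps its interviews, its record review or its place in the analysis.

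On the analysis side, section 4.1 states "Analyses will use intention-to-treat" and section 9.4.1 states "Primary analysis will use intention-to-treat analysis"; the administrative supplement analysis repeats this for the Hispanic/Latino dyads. The term is not defined in any of these places. The section headed "9.3 POPULATIONS FOR ANALYSES" contains only N/A.

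On masking, section 4.1 says "as in most behavioral interventions clinicians and participants cannot be masked to study arm", while section 6.3 says that the overall principal investigator "will remain masked to study arm assignments to minimize bias in study procedures and analysis".

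**The concern.** Intention-to-treat governs how collected data are analysed. It cannot restore an interview that was never held. Section 7.1 is headed as discontinuation of the intervention but deals only with interim analyses and stopping rules. The protocol therefore has no stated category for a dyad that stops the intervention while its outcomes are still collected.

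The two permissions differ in reach. Non-adherence can arise mainly in the intervention arm, where section 6.2.1 tracks four components; control dyads receive educational material and usual care (section 6.1). Non-start can occur in either arm. Site investigators probably know the arm when they decide on discontinuation. That is an inference from sections 4.1 and 6.2.1, not a statement in the protocol. Section 9.2, by contrast, plans for dropout that is equal between groups and names only death and withdrawal.

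Most exposed are the secondary outcomes obtained only from the caregiver. Section 9.4.1 provides multiple imputation only for dichotomous 60-day outcomes, and only when more than 10% are missing. It specifies none for the continuous interview scales.

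**Working it through.** **1. The plan's own figures.** Section 9.2: 424 × 0.85 = 360.4, hence 360 (180 per arm); 424 × 0.75 = 318 = 2 × 159. Both agree with the plan.

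For the primary outcome, Table 3 gives a control rate of 0.53 and differences of 0.25 and 0.2, so intervention rates of 0.28 and 0.33. With a Wald test on the log rate ratio:

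SE = √[φ(1/(nλ₀) + 1/(nλ₁))], power = Φ(|ln(λ₁/λ₀)|/SE − 1.96).

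- φ = 1 gives 0.956 and 0.818 at n = 180 (stated 0.96, 0.82), and 0.931 and 0.769 at n = 159 (stated 0.95, 0.79).
- The overdispersion factor is not stated. Solving for it from the four overdispersed powers (0.81, 0.60, 0.76, 0.55) gives φ = 1.667, 1.677, 1.668 and 1.669. I use 1.67.

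**2. What is lost if follow-up stops.** From the schedule in section 1.2:

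| Source | Outcome rows |
|---|---|
| Interviews only (6 of 10 secondary rows) | SM-EOLD, NPI-Q, post-acute palliative care or hospice use, shared decision-making, Family Distress, Zarit |
| Record review only (4 of 10) | Palliative Care Domain Index, nursing home transition, prognosis discussion, goals-of-care decision-making |
| Both | Hospital and ED transfers (primary) |

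The record-review list in section 8.1 contains none of the six interview-only outcomes. It does contain ED visits and readmissions within 60 days.

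**3. Effect on the primary test with no true effect (illustration).** Assumptions, none from the documents: a share f of the intervention arm is removed and none of the control arm; removed dyads lose all primary-outcome data; their transfer rate is m times that of the rest of the arm. Then

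expected IRR = 1/[(1 − f) + f·m].

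With δ = ln(IRR)/SE, two-sided error = Φ(−1.96 − δ) + 1 − Φ(1.96 − δ).

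Example, f = 0.07 and m = 2: IRR = 1/1.07 = 0.935. With 180 × 0.53 = 95.4, SE = √[1.67(1/95.4 + 1/(95.4 × 0.935))] = 0.190, δ = −0.355, and the error is 6.5%.

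| f (dyads of 212) | IRR, m = 0.5 | IRR, m = 1 | IRR, m = 1.5 | IRR, m = 2 | Two-sided error, range |
|---|---|---|---|---|---|
| 2% (about 4) | 1.010 | 1.000 | 0.990 | 0.980 | 5.0–5.1% |
| 5% (about 11) | 1.026 | 1.000 | 0.976 | 0.952 | 5.0–5.8% |
| 7% (about 15) | 1.036 | 1.000 | 0.966 | 0.935 | 5.0–6.5% |

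These assume full replacement (180 analysed in the intervention arm). With no replacement, 180(1 − f) analysed, the worst cell is 6.4% instead of 6.5%. In the same formula with m = 2, f = 10% gives IRR 0.91 and 7.9%, and f = 20% gives 0.83 and 15%.

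**4. Power cost of keeping these dyads (illustration).** On the difference scale, power = Φ(|λ₀ − λ₁|/√[φ(λ₀ + λ₁)/n] − 1.96). An assumed φ of 1.7 gives 0.815 at n = 180 for the difference of 0.25 (stated 0.81). If 5% of the intervention arm gets no benefit, its rate is 0.53 − 0.25 × 0.95 = 0.2925 and power is 0.769. At 10% the rate is 0.305 and power is 0.717. The log scale with φ = 1.67 gives nearly the same: 0.809, 0.764 and 0.714.

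**The case against.** The strongest reply is that the plan already points to keeping these dyads. Intention-to-treat, on its usual meaning, counts every randomized dyad in its assigned arm. Section 8.1 makes data collection the same in both arms. Section 4.4 ends the study only when the record review is complete for every dyad. The offset in section 9.4.2 keeps dyads with 30-day data only, and its dose analysis, from 0 to 4 components, expects partly treated dyads in the data. The stated response to low fidelity in section 6.2.1 is feedback to the site, not removal. Reasons for discontinuation are already recorded on the case report form.

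Much of this stands, and it rules out several stronger readings that a reader might infer:

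- *That 7.2 contradicts intention-to-treat, or that these dyads are excluded from analysis.* No passage excludes them. The defect is a permission that nothing limits.
- *That replacement drops the original dyad.* The sentence only allows another to be added, and step 3 shows that replacement itself hardly matters. Any bias comes from lost data.
- *That the emphasis on 60-day interviews in section 8.1 weakens the record review as a source for the primary outcome.* That sentence contrasts the 60-day with the 30-day interviews.
- *That the pilot fidelity of 77% to 93% (section 4.3) or the 80% fidelity threshold indicates a removal rate.* Both concern delivery of the intervention.

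What the reply does not supply is any statement that interviews continue after discontinuation from the study. In the same list, 7.2 includes loss to follow-up and cases where further data collection is against the participant's interest. So the natural reading of discontinuation there is that collection stops.

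**Conclusion.** The point holds as an unlimited permission that should be closed before it is used. Its main consequence is loss of interview-only secondary outcomes, mainly in the intervention arm. The documents give no basis for sizing that loss.

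For the primary test the effect is small across the assumed removal rates of 2% to 7%: negligible at 2%, and at most 6.5% two-sided error at 7%. It grows only if removal is well above that. The calculation deliberately assumes removal in one arm only and complete loss of primary data, although the record review should retain at least part of those data. The direction of bias depends on whether removed dyads have more or fewer transfers than the rest, and the documents do not say. A claim that the primary result would be biased in favour of the intervention is therefore not supported.

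**What to change.** - In 7.2, delete intervention non-adherence as a reason for discontinuation from the study, or state that it does not by itself end outcome collection.
- State that non-adherent and non-starting dyads continue with the 30- and 60-day interviews and the record review, unless consent is withdrawn or the existing best-interest reason in 7.2 applies.
- State that replacement adds dyads and removes none: the original dyad is still followed and counted in its assigned arm.
- Replace N/A in 9.3 with all randomized dyads, analysed as randomized, and use that as the definition of intention-to-treat.
- Report non-starters and discontinuations by arm, with the reasons already recorded on the case report form.

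The cost is protocol wording and a few more interviews; the record review is already planned. The estimated effect will be somewhat diluted, and power somewhat lower, compared with an analysis that omits these dyads (step 4). The change concerns data collection and analysis only, not care.
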